## 6.4 STUDY INTERVENTION ADHERENCE

### 6.4.1 BRIGHT

Adherence of subjects to BRIGHT study procedures are key to ensure scientific rigor, validity, reproducibility, and achievement of study objectives. Adherence will be assessed with the following

measures: 1) attendance at intervention visits; 2) duration of study visits; 3) homework completion, 4) psychologist rating of patient engagement and material comprehension. Attendance at all study visits are mandatory to remain an active participant. Adherence information will be ascertained from the BRIGHT visit note authored by the study psychologist in a patient-adherence tracking log in the EMR after each study visit and documented in the eCase Report Form (eCRF) after each study visit by the study coordinator.

#### 6.4.2 AC

Adherence of subjects to AC study procedures are key to ensure matching of the delivery format, frequency, duration, and schedule of the control, and thus scientific rigor, validity, reproducibility, and achievement of study objectives. Adherence to AC will be assessed with the following measures: 1) attendance at intervention visits; 2) duration of study visits; and 3) homework completion. Attendance at all study visits are mandatory to remain an active participant. Adherence information will be ascertained by the study coordinator after each study visit and documented in the eCRF.

### 6.5 CONCOMITANT THERAPY

For this protocol, participants may use antidepressants and anxiolytics at the discretion of their treating providers. Medication usage will be assessed at each study visit and documented in the eCRF.

#### 6.5.1 RESCUE THERAPY

N/A

## 7 STUDY INTERVENTION DISCONTINUATION AND PARTICIPANT DISCONTINUATION/WITHDRAWAL

### 7.1 DISCONTINUATION OF STUDY INTERVENTION/EXPERIMENTAL MANIPULATION

At subject, PI, or study team member request.

When a subject discontinues from BRIGHT or AC but not from the study, remaining study procedures will be completed as indicated by the study protocol. If a clinically significant finding is identified (including, but not limited to changes from baseline) after enrollment, the investigator or qualified designee will determine if any change in participant management is needed. Any new clinically relevant finding will be reported as an adverse event (AE).

The data to be collected at the time of study intervention discontinuation will include the following:

- The reason(s) for discontinuing the participant from the intervention, and methods for determining the need to discontinue
- If the participant is due to complete assessments within 2 weeks of being discontinued from the study intervention, those assessments will be administered at the time of discontinuation; if the next scheduled assessments are more than 2 weeks from the discontinuation date, the discontinued

participant will wait for the next scheduled assessment. Thereafter, the participant will be included in all future scheduled assessments, even though not participating in the intervention.

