### 1.3 SCHEDULE OF ACTIVITIES

	Pre Screen (-60 to 1)	Visit 1 Day 1 a	Visit 2 Day 8 ±14	Visit 3 Day 15 ±7	Visit 4 Day 22 ±7	Visit 5 Day 29 ±7	Visit 6 Day 36 ±7	Visit 7 Day 43 ±14	Visit 8 Day 64 ±14	Visit 9 Day 124±14	For Details, see section
Informed Consent											
Review Study Eligibility b	X										5
Informed Consent c	X										10.1.1
Study Procedures											
Randomization		X									6.3
Demographics		X									8.1
Clinical and Oncologic History		X									8.1
ASI-R		X									8.1
Monitoring											
AS/SAE Assessment			X	X	X	X	X	X	X	X	8.3
Medication Assessment			X	X	X	X	X	X	X	X	8.3
Intervention Administration											
BRIGHT or AC			X	X	X	X	X				6.1
Efficacy Evaluation											
Body Image Scale d	X							X	X	X	8.1
IMAGE-HN d		X						X	X	X	8.1
PROM Assessments											
BICSI d		X						X	X	X	8.1
Shame and Stigma Scale d		X							X	X	8.1
PROMIS SF v1.0- Depression 8a d		X							X	X	8.1
PROMIS SF v1.0- Anxiety 8a d		X							X	X	8.1
PROMIS SF v2.0- Social Isolation 8a d		X							X	X	8.1
PROMIS SF v2.0- Social Roles 8a d		X							X	X	8.1
EORTC QLQ-HN35 d		X							X	X	8.1
Other Evaluations											

Intervention Fidelity		X	X	X	X	X					6.2
Patient Adherence			X	X	X	X					6.4
Program Evaluation								X			8.1
WAI-SR				X			X				8.1

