### 3 OBJECTIVES AND ENDPOINTS

Table 3. Study Objectives and Endpoints	
OBJECTIVES	ENDPOINTS
Primary	
To assess the clinical efficacy of BRIGHT compared with AC on BID in HNC survivors as determined by change in BIS scores at 1-month post-intervention relative to baseline	Change in BIS score from baseline to 1-month post-intervention
Secondary	
To assess the clinical efficacy of BRIGHT compared with AC on BID in HNC survivors as determined by change in IMAGE-HN scores at 1-month post-intervention relative to baseline and 3-months post-intervention relative to baseline	Change in IMAGE HN Scores from baseline to 1-month post-intervention and from baseline to 3-months post-intervention
To explore the behavioral mechanism of action of BRIGHT on changes in BID in HNC survivors as measured by the change in BICSI scores at 1-week post-intervention relative to baseline.	Change in BICSI scores from baseline to 1-week post-intervention

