## 7.3 LOST TO FOLLOW-UP

A participant will be considered lost to follow-up if he or she fails to return for two scheduled visits and study staff are unable to contact the participant after at least 3 attempts.

The following actions must be taken if a participant fails to return to the clinic for a required study visit:

- The site will attempt to contact the participant, reschedule the missed visit within 2 weeks, counsel the participant on the importance of maintaining the assigned visit schedule and ascertain if the participant wishes to and/or should continue in the study
- Before a participant is deemed lost to follow-up, the investigator or designee will make every effort to regain contact with the participant (where possible, 3 telephone calls and, if necessary, a certified letter to the participant's last known mailing address or local equivalent methods). These contact attempts will be documented in the participant's medical record or study file.
- Should the participant continue to be unreachable, he or she will be considered to have withdrawn from the study with a primary reason of lost to follow-up.

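### Section 7.1 brings forward the 1-week questionnaires of patients who stop the intervention late (Day 29–43) by up to 14 days, apparently in place of the scheduled visit, and the analysis has no rule for these records

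*Combined protocol and SAP*

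**What the plan says.** Section 7.1 separates stopping the intervention from leaving the study. For a patient who stops but stays in, it sets a two-way rule. If the patient is due for "assessments within 2 weeks of being discontinued from the study intervention, those assessments will be administered at the time of discontinuation". If the next assessment is further away than that, the "participant will wait for the next scheduled assessment". The section then adds: "Thereafter, the participant will be included in all future scheduled assessments, even though not participating in the intervention".

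The Schedule of Activities (Section 1.3) gives the last two sessions as "Visit 5 Day 29 ±7" and "Visit 6 Day 36 ±7". The 1-week assessment (Visit 7: BIS, IMAGE-HN, BICSI) is at Day 43 ±14. The 1-month assessment (Visit 8, with the primary BIS) is at Day 64 ±14. For a missed visit, Section 7.3 tells the site to "reschedule the missed visit within 2 weeks".

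The primary endpoint in Section 3 is "Change in BIS score from baseline to 1-month post-intervention". Section 9.4.2 models BIS change at 1 week, 1 month and 3 months. Section 9.4.3 uses BICSI change at 1 week as the mediator of BIS change at 1 month. Neither Section 9.3 nor Section 9.4 says how to label or analyse an assessment moved under Section 7.1.

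**The concern.** The timing of an outcome should not depend on what a patient does after randomisation, and here it does. Patients who stop shortly before Visit 7 are measured on the day they stop; everyone else is measured around Day 43. The trial is open-label and the arms ask different things of patients (60-minute CBT sessions against 30-minute videos), so the frequency and timing of stopping could differ by arm.

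The content of the measurement changes as well. Section 8.1 says that the BIS asks about the previous 7 days. A BIS completed on the stopping day therefore describes only time up to stopping, with no period after the intervention, but could be analysed as a 1-week post-intervention value. The same holds for the timing of BICSI, where the mediation argument needs coping measured after the intervention. If the early record replaces Visit 7, the value at the defined time is given up although the patient is still in follow-up.

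**Working it through.** The plan gives no figure of its own on this point, so the check applies the rule in Section 7.1 to the dates in Section 1.3.

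**Inputs (nominal days from Section 1.3).** Sessions 1 to 5: Days 8, 15, 22, 29, 36, with session 5 at ±7. Visit 7: Day 43 ±14. Visit 8: Day 64 ±14. Threshold from Section 7.1: 2 weeks = 14 days.

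**Rule.** Gap = scheduled assessment day − stopping day. If 0 ≤ gap ≤ 14, the assessment is given on the stopping day and is early by the gap. If gap > 14, the patient waits.

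**Step 1: the 1-week assessment (Day 43).**

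| Stopping day | Gap to Day 43 | Result |
|---|---|---|
| 8 (session 1) | 43 − 8 = 35 | waits |
| 15 (session 2) | 43 − 15 = 28 | waits |
| 22 (session 3) | 43 − 22 = 21 | waits |
| 28 | 43 − 28 = 15 | waits |
| 29 (session 4) | 43 − 29 = 14 | moved, 14 days early |
| 36 (session 5) | 43 − 36 = 7 | moved, 7 days early |
| 43 | 43 − 43 = 0 | no shift |

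Only stops on Day 29 to 43 are affected, by 14 down to 0 days.

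**Step 2: the window.** Visit 7 runs from 43 − 14 = Day 29 to 43 + 14 = Day 57. Even the largest shift falls on the opening day of the window and would not count as out of window.

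**Step 3: the recall period.** At Day 43 the 7-day recall of the BIS starts at 43 − 7 = Day 36, the nominal day of the last session. At Day 29 it starts at 29 − 7 = Day 22, so all of it precedes stopping.

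**Step 4: the primary 1-month BIS (Day 64).** The latest session 5 within its window is 36 + 7 = Day 43, and 64 − 43 = 21 > 14, so nothing moves. The rule reaches Visit 8 only for a stop on Day 50 or later:
- session 5 missed on Day 36 and rescheduled by 14 days: 36 + 14 = 50, and 64 − 50 = 14, moved;
- session 5 missed on Day 43 and rescheduled by 14 days: 43 + 14 = 57, and 64 − 57 = 7, moved.

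Both cases need the patient to stop at the rescheduled session and Visit 8 to stay at Day 64. If Visit 8 is instead timed from the actual last session, at the nominal distance of 64 − 36 = 28 days, a patient who stops on the day of that session is 28 days away and waits. The documents do not say which anchor applies.

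**Step 5: replacement or addition.** Section 7.1 gives the due assessment at stopping and then refers only to future scheduled assessments. Nothing says that the assessment just given is repeated at its scheduled date. Replacement is therefore the natural reading, but it is not stated outright.

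**The case against.** The strongest reply is that the rule creates no timing which the schedule does not already permit. Any participant may complete Visit 7 as early as Day 29, and a patient who stops on Day 28 could be assessed the next day within the window. This stands as far as it goes: the moved records are not out of window. But the window is symmetric and open to everyone, whereas the shift under Section 7.1 is in one direction and triggered by stopping. Being in window also means that no one would notice it.

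Three stronger readings are tempting, and the documents do not support them.
- A reader might infer that early stoppers in general are measured too soon. On nominal dates, those who stop at sessions 1 to 3 wait for Visit 7.
- A reader might infer that the primary 1-month BIS is routinely taken early. That needs a last session run past its ±7-day window, a stop at that session, and Visit 8 held at Day 64. Fixed dates would also put the nominal 1-week visit (Day 43) before a session 5 held on Day 50.
- A reader might apply an assumed stopping rate of 5–15% to all 52 patients and conclude that 3 to 8 are affected (0.05 × 52 = 2.6; 0.15 × 52 = 7.8). The documents give no such rate, and the count would include patients who stop before Day 29.

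Homework is not a contrast between the arms either, since Section 6.4.2 lists homework completion for the control arm too.

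Other mitigation is real. The pilot reported all 45 sessions completed and one dropout in 10. Sections 6.4 and 7.2 may take some non-adherent patients out of the study altogether. The per-protocol analysis in Section 9.3 is limited to patients who completed all five sessions, and the mediation analysis is labelled exploratory. Collecting data when a patient stops is also a sensible guard against losing contact. None of this tells the analyst what to do with a stopping-day record in the main analysis.

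**Conclusion.** The point holds in a narrow form and is minor. For patients who stop on Day 29 to 43 and stay in the study, the 1-week BIS, IMAGE-HN and BICSI are taken 0 to 14 days early, on the stopping day, and Section 9 has no rule for them. The number is unknown and probably small; with 22 evaluable patients per arm, each one is 1/22 = 4.5% of an arm.

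The effect falls mainly on the 1-week contrast and the mediator. The 1-week BIS does enter the primary model, but with time treated as categories and complete data it does not shift the estimated 1-month contrast. The primary BIS itself moves only in the edge case of step 4.

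The conclusion rests on two assumptions: follow-up days are counted from Day 1 as printed in Section 1.3, and the stopping-day assessment replaces the scheduled one. If the second is wrong, what remains is an unclear sentence and a missing rule for the extra record. The sample size calculation is not affected.

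**What to change.** Change Section 7.1 so that patients who stop the intervention keep Visits 7, 8 and 9 at their scheduled times, collected remotely where needed, as footnote d of Section 1.3 already allows by mail or email. Record any questionnaire taken at discontinuation as an additional, unscheduled assessment that does not replace the scheduled value when that value is obtained. State in Section 9.4 how the unscheduled record is used if the scheduled value is missing. It would help to say in Section 1.3 whether follow-up visits are counted from Day 1 or from the last session, since this decides whether Visit 8 can be touched at all.

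The cost is a few sentences and an unscheduled-visit form. The burden is at most one extra questionnaire set for a few patients. The benefit of the present rule, an early record in case contact is lost, is kept.

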## 7.2 PARTICIPANT DISCONTINUATION/WITHDRAWAL FROM THE STUDY

Participants are free to withdraw from participation in the study at any time upon request. The investigators will seek to minimize participant discontinuation/withdrawal from the study (see **Section 7.3, Lost to Follow-Up**) except for safety reasons.

An investigator or the IRB may discontinue a participant from the study for the following reasons:

- Significant study intervention non-compliance
- Lost-to-follow up; unable to contact subject (see **Section 7.3, Lost to Follow-Up**)
- Any event or medical condition or situation occurs such that continued collection of follow-up study data would not be in the best interest of the participant or might require an additional treatment that would confound the interpretation of the study
  - Subjects who are enrolled into the study and undergo a significant HNC ablative or reconstructive surgery (defined by a postoperative inpatient stay of at least three days) during the study intervention or follow-up period
  - Subjects who are enrolled in the study and develop a recurrence of their index HNC (local, regional or distant recurrence, radiologic or biopsy-proven) or metachronous second primary cancer (radiologic or biopsy-proven) during the study intervention or follow-up period

The rationale for having these patients discontinue the study is that a significant HN-related surgery, development of a HNC recurrence, or development of a second primary cancer may introduce new body image concerns, confounding the association between BRIGHT (or AC) and changes in BID.

The reason for participant discontinuation or withdrawal from the study will be recorded on the CRF. Subjects who sign the informed consent form and are randomized, regardless of whether or not they received the intervention, will not be replaced.

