#### Secondary Endpoints

##### *Behavioral Mediator*

Change in Body Image Coping Strategies Inventory (BICSI) scores. The BICSI is a 29-item validated measure of the cognitive and behavioral responses to manage threats to body image. BICSI contains three sub-domains; 1) appearance fixing (altering appearance by covering, camouflaging, or correcting the perceived defect), 2) avoidance (an attempt to escape or avert stressful body-image situations), and 3) positive rational acceptance (acceptance of the challenging event and positive self-care or rational self-talk about one's appearance). Items are scored on a 4-point Likert scale from 'definitely not like me' to 'definitely like me' (0-3). The scores for each subscale are calculated by summing the values for the individual questions and thus range as follows: 1) appearance fixing (0-30), 2) avoidance (0-24), 3) positive rational acceptance (0-33). For each subscale, higher scores indicate greater quantities of each conceptual domain (appearance fixing, avoidance, and positive rational acceptance). Avoidance and appearance fixing are maladaptive means of coping that are associated with dysfunctional schemas, elevated levels of BID and

distress, and poorer psychosocial functioning. Positive rational acceptance is a positive means of coping that is associated with lower levels of BID and distress.

*Clinical Activity*

Change in IMAGE-HN scores: The IMAGE-HN is a psychometrically sound, 24-item, multi-domain PROM consisting of 4 sub-scales and a global scale that can be used to measure key aspects of HNC-related BID due to HNC or its treatment. Responses include 'Never', 'Rarely', 'Sometimes', 'Often', 'Always', corresponding to a Likert scale of 0-4, respectively. Total IMAGE-HN scores on the global domain (21 questions) range from 0-84, with higher scores indicated greater HNC-related body image dissatisfaction. Raw scores for each sub-scale as well as the global scale can be converted to scaled scores for each, which range from 0-100 with higher scores representing greater HNC-related BID.

Response. Response is defined as a BIS score at 1-month post-intervention that is lower than the BIS score at baseline.

*Secondary Measures of Psychosocial Wellbeing*

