
**Fig. 4. Power Calculations for (A)** Mean difference in  $\Delta$  in Body Image Scale scores between baseline and 1-month post intervention, comparing BRIGHT and AC; **(B)** standardized effect, comparing  $\Delta$  in Body Image Scale scores between BRIGHT and AC from baseline to 1-month post intervention

early stage of development (single-site pilot RCT) to ensure follow-up on promising interventions to guide and power a subsequent larger RCT to fully evaluate the efficacy of BRIGHT as a treatment of BID in HNC survivors (i.e. test BRIGHT with significance level of 0.05). We therefore consider our RCT to be appropriately and rigorously designed to detect a clinically meaningful reduction in BID.

In order to have 44 patients eligible for the efficacy analysis in the modified ITT population (see **Section 9.3, Population for Analyses**), we plan to enroll 52 patients. Our sample size is inflated by 20% based on interim accrual data. This inflation account for study dropout and the predictable subset of patients would be enrolled in the study, be randomized to BRIGHT or AC, receive a portion or all of the intervention and then subsequently are withdrawn from the study and non-evaluable due to a major HNC surgery or recurrent or second primary cancer.

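### Section 7.2 lets randomised patients be taken out of follow-up after surgery, recurrence or a second primary on the ground of confounding, but events after randomisation cannot confound the BRIGHT versus AC comparison

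*Combined protocol and SAP*

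**What the plan says.** Section 7.2 opens its list with a permission: "An investigator or the IRB may discontinue a participant from the study for the following reasons". One listed ground is an event or condition after which "continued collection of follow-up study data would not be in the best interest of the participant", or which might need additional treatment that would confound interpretation. Two cases sit under it: major head and neck surgery, and recurrence or a "metachronous second primary cancer (radiologic or biopsy-proven) during the study intervention or follow-up period". The rationale for these two cases is that they "may introduce new body image concerns, confounding the association between BRIGHT (or AC) and changes in BID".

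Section 9.2 treats the permission as carried out. It raises enrolment to 52 to keep 44 in a modified ITT set, allowing for dropout and for patients who have part or all of the intervention and are then "withdrawn from the study and non-evaluable due to a major HNC surgery or recurrent or second primary cancer". The version history links the rise from 48 to 52 to recurrent and second primary cancers.

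Section 9.3 first counts everyone randomised as evaluable, then names the same two subsets. It does not say whether their data are excluded, used up to the event, or imputed. Section 9.2 plans multiple imputation for missing data but does not link it to these patients.

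Section 7.1 handles patients who stop only the intervention in the opposite way: "the participant will be included in all future scheduled assessments, even though not participating in the intervention".

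**The concern.** A confounder of a treatment comparison must be associated with allocation other than as a consequence of it. Randomisation removes such associations apart from chance. Surgery, recurrence or a second primary after randomisation belongs to the course that follows allocation. It is an intercurrent event: it may add variance or change what the comparison means, but it cannot confound it.

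Acting on the rationale makes the evaluable set depend on what happens after allocation. It also makes it depend on a discretionary decision in a trial that section 4.1 describes as non-blinded. If removals are alike in number and prognosis in the two arms, the cost is information and a result limited to event-free patients. If they differ, the primary contrast can be biased. Because BIS is not collected after discontinuation, a later all-randomised analysis would have to rest on imputation assumptions that the trial's own data cannot test. Section 4.2 says this trial is meant to supply effect-size estimates for a definitive trial, so any distortion would carry forward.

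**Working it through.** **Inputs.** From 9.2: 52 enrolled, 44 evaluable (22 per arm), mean improvement 0.2 (SD 5.9) in AC and 4.6 (SD 3.9) in BRIGHT, pooled SD 5.62, standardized effect 0.78, two-sided alpha 0.10, stated power 80.2%. From 6.3: 1:1 allocation, so 26 per arm if equal. From 1.3: BIS after the intervention at Visit 7 (Day 43), Visit 8 (Day 64, the 1-month primary time) and Visit 9 (Day 124).

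**The plan's own figure.** Noncentral-t power with 22 per arm, effect 0.78, 42 degrees of freedom and alpha 0.10 is 81.6%, against the stated 80.2%. The figure is reproduced to within 2 points.

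**Information lost.** (52 − 44)/52 = 8/52 = 15.4%. The standard error scales with 1/√n, so the interval widens by √(52/44) = 1.087, or 8.7%. Both are upper bounds for this rule. The 8 include ordinary dropout, and the documents do not give the split.

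**When the event matters.** The window in 7.2 runs through follow-up. An event after Visit 8 comes after the primary BIS has been collected, so stopping then costs only 3-month data. The plan does not say whether the 1-month value is still used.

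**Possible bias (assumed inputs).** Let k_B and k_A patients be removed from 26 per arm, with outcomes m BIS points worse than the rest of their arm. The retained difference then exceeds the all-randomised difference by m(k_B − k_A)/26. Assuming m of 3 to 8:

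| Removed, BRIGHT/AC | Shift in difference (BIS points) |
|---|---|
| 4/4 | 0 |
| 5/3 | 0.2 to 0.6 |
| 6/2 | 0.5 to 1.2 |
| 7/1 | 0.7 to 1.8 |

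At 6/2 the shift is 10-28% of the planned 4.4 points (0.46/4.4 to 1.23/4.4). With more removals in AC the sign reverses and BRIGHT's advantage shrinks.

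**Power if everyone is kept (assumed inputs).** Take 26 per arm with 4 event patients in each, and alpha 0.10. In the favourable case event patients keep the full 4.4-point benefit and do not worsen. In the unfavourable case they have no benefit and are 5 points worse in both arms, so the difference falls to 4.4 × 22/26 = 3.7. Two SDs are shown because the stated arm SDs pool to √((5.9² + 3.9²)/2) = 5.00 at equal n, while 9.2 gives 5.62. The unfavourable case was simulated.

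| SD | 22 event-free per arm | All 26 per arm, unfavourable to favourable |
|---|---|---|
| 5.0 | 89% | 78% to 93% |
| 5.62 | 82% | 70% to 87% |

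If the number of events is allowed to vary around 4 per arm, the lower ends become about 75% and 68%.

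**The case against.** The strongest reply has five parts.

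- **A permission, not a requirement.** Section 7.2 says discontinuation may happen, and adds that investigators will try to keep it to a minimum. A reader might infer that collection must stop after every such event. The text does not say that, although 9.2 counts these patients as withdrawn.
- **A second ground.** The participant's best interest is also cited. It is legitimate and does not depend on the confounding argument, so it should stay.
- **Arm-dependence is not shown.** A reader might infer that BRIGHT changes the surgery rate, because the mediator section of 8.1 defines appearance fixing as "altering appearance by covering, camouflaging, or correcting the perceived defect" and coping is what BRIGHT targets. That passage describes a questionnaire subscale, not surgery with an inpatient stay of three days or more. Inclusion criterion 6 already keeps out patients with such surgery planned, and the version history points to recurrence and second primaries. The documents offer no route from five sessions to recurrence and no event rates by arm.
- **Other analyses remain possible.** A reader might infer that no all-randomised or sensitivity analysis could be done. That goes too far. The mixed model in 9.4.2 can use BIS collected before the event, and delta-adjusted or tipping-point imputation could be added. These would rest on assumptions rather than observed post-event scores.
- **A different estimand.** The effect in the absence of recurrence or surgery is a defensible target for a pilot meant to isolate the content of BRIGHT. It would have to be stated, and it is not.

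All five narrow the point. None makes a post-randomisation event a confounder or supplies the uncollected scores.

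**Conclusion.** The confounding rationale in 7.2 is wrong, and with 9.2 it allows primary outcomes of randomised patients to go uncollected for a reason that does not justify it. The certain part of the cost is modest: at most 8 of 52 patients (15.4%) and an interval at most 8.7% wider, less once dropout and events after the 1-month visit are taken out. Bias is a possibility that the documents neither establish nor exclude. The shift of 0.5 to 1.2 points assumes a 6/2 split and removed patients 3 to 8 points worse; an even split under the same model gives none. Nor do the documents support assuming that retention always raises power, since the all-randomised analysis can fall below 80% if event patients gain little from BRIGHT. This is a change worth making because it is cheap, not because the trial has been shown to be biased.

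**What to change.** **Section 7.2.** Delete the confounding rationale. Keep the best-interest ground and the right to withdraw. Record the type and date of each event. Where the participant agrees, still collect BIS and IMAGE-HN at the remaining visits among Visits 7-9. No comment is made on whether the intervention continues.

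**Sections 9.2, 9.3 and 9.4.2.** State the estimand, including how these events are handled. Report an analysis of all randomised patients using every BIS, beside one that drops only BIS values dated after the event. Make the non-evaluable wording in 9.2 agree with this.

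**Cost.** Protocol wording, and a few questionnaires in at most about 8 patients, which section 1.3 already allows by mail or email. The statistical price is that post-event scores may add noise or dilute the effect, with the power ranges shown above. The event-censored analysis stays available, so the result for event-free follow-up is not lost.
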